7.5.3 Pharmacokinetic parameters

Handling of missing PK data will be performed according to the relevant SOP of the Sponsor ([001-MCS-36-472](#)).

For the non-compartmental analysis, concentration data identified with NOS, NOR or NOA will generally not be considered. Concentration values in the lag phase identified as BLQ or NOP will be set to zero. All other BLQ/NOP values of the profile will be ignored. The lag phase is defined as the period between time zero and the first time point with a concentration above the quantification limit.

Descriptive statistics of parameters are calculated only when a parameter value is available for certain for at least 2/3 of the treated individuals. If the actual sampling time is not recorded or is missing for a certain time point, the planned time will generally be used for this time point instead. PK parameters that cannot be determined will be identified as “not calculated”.

7.6 RANDOMISATION

Subjects will be randomized to one of the two treatments in a 1:1 ratio. The block size will be documented in the CTR.

The sponsor will arrange for the randomization as well as packaging and labelling of trial medication. The randomization list will be generated using a validated system, which involves a pseudo-random number generator and a supplied seed number so that the resulting allocation is both reproducible and non-predictable. Randomization will be stratified by:

- site (2 levels and for logistical reasons only)
- baseline body weight category with ranges:
 - low: ≤ 60.0 kg
 - medium: > 60.0 to ≤ 90.0 kg
 - high: ≥ 90.0 kg

and will be randomized sequentially (the lowest sequentially available randomization number).

The randomization list will contain additional blocks to allow for subject replacement (refer to [Section 3.3.5](#)).

7.7 DETERMINATION OF SAMPLE SIZE

It is planned to enter a total of 160 subjects for the primary analysis of this trial, because this sample size is considered sufficient to assess the primary objective of this exploratory trial. With this sample size, the precisions of the ratio of the geometric means (test/reference) to be expected with 95% probability, are presented in [Table 7.7: 1](#). That is to say, we expect with 95% probability, that the precision is no greater than the value specified, where precision is defined as the ratio of upper CI limit to the point estimate of the geometric mean ratio.

Proprietary confidential information © 2016 Boehringer Ingelheim International GmbH or one or more of its affiliated companies

The observed ratio of the geometric means (and geometric coefficient of variation (gCV)) in previous trials (1297.8, [c03070713](#); 1297.6, CTR in reporting stage) were:

- 108% (45%) for $AUC_{(0-\infty)}$ in 1297.8
- 104% (54%) for $AUC_{(0-\infty)}$ in 1297.6
- 112% (32%) for C_{max} in 1297.6

The values from 1297.6 are estimated from the models adjusted for BMI (continuous). Although the main analysis for this study will be adjusted for baseline body weight (continuous), these model estimates serve as a good approximation, given the high correlation expected between BMI and body weight. The values coming from 1297.8 are unadjusted.

Table 7.7: 1 Precision and illustrative two-sided 90% confidence intervals around the ratios of geometric means (T/R) for different gCVs in a parallel trial (N=160).

gCV [%]	Precision upper CL / relative BA estimate	Ratio [%] *	Lower CL [%]	Upper CL [%]
32	1.09	112	102.44	122.45
45	1.13	108	95.53	122.09
54	1.16	104	90.01	120.17

*Ratio of geometric means (test/reference) for a PK endpoint is defined by $\exp(\mu_T)/\exp(\mu_R)$.

The calculation was performed as described by Julious ([R12-0972](#)) using R Version 3.2.2.

Regarding the assessment of the primary PK parameters, albeit in an exploratory manner, the following table ([Table 7.7: 2](#)) provides an overview of the probability of success (power) given some assumed effect sizes and assumptions on the gCV, as described above. The calculations are based upon the overall treatment effect, adjusting for BMI continuous (as a good substitute for body weight), where data is available.

Boehringer Ingelheim
BI Trial No.: 1297.13
c11534380-01

23 Aug 2016

Trial Protocol

Page 50 of 58

Proprietary confidential information © 2016 Boehringer Ingelheim International GmbH or one or more of its affiliated companies

Table 7.7: 2 Power (%) for concluding bioequivalence (acceptance range 80-125%) based on a geometric coefficient of variation around 50% and for different expected ratios of geometric means (test/reference) in a parallel trial (N=160).

gCV [%]	Ratio [%] [*]			
	100	104	108	112
32	>99%	98%	90%	71%
45	89%	83%	68%	55%
50	81%	75%	61%	-
54	74%	68%	55%	-

^{*}Ratio of geometric means (test/reference) for a PK endpoint is defined by $\exp(\mu_T)/\exp(\mu_R)$.

The calculations were performed using nQuery Version 2.0.1.0.

Therefore, with the expectation that there is less variability in this planned trial, there should be more than 70% power to have the resulting 90% confidence interval of the ratio of the gMeans lying within the range of 80-125%. The reason for less expected variability is that the drug is now to be administered in the thigh, and there is also expected to be slightly less variability when adjusting for baseline body weight.

Thus a total sample size of up to 160 subjects is planned for this trial and with no planned adjustment for drop-outs.

Boehringer Ingelheim
BI Trial No.: 1297.13
c11534380-01

23 Aug 2016

Trial Protocol

Page 51 of 58

Proprietary confidential information © 2016 Boehringer Ingelheim International GmbH or one or more of its affiliated companies

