7.3.1 Primary endpoint analyses

In an exploratory manner, the relative bioavailability of BI 695501 using autoinjector (A) compared to BI 695501 using prefilled syringe (B) will be estimated by the ratios of the geometric means (A/B) for the primary PK endpoints. Point estimates of relative bioavailability, the ratios (A/B) of the geometric means for the primary PK endpoints (see [Section 5.1.1](#)), and their two-sided 90% CIs will be provided for the overall comparison A versus B.

The PK endpoints will be log-transformed (natural logarithm) prior to fitting the ANOVA model (see [Section 7.1](#)). For each PK endpoint, the difference between the means for $\log(A)$ - $\log(B)$ will be estimated by the difference in the corresponding adjusted means (least-squares means), and a two-sided 90% CI based on the t-distribution will be computed. These quantities will then be back-transformed to the original scale to provide the point estimate and 90% CIs for the corresponding ratio of geometric means (A/B) for each PK endpoint.

The ANOVA will be conducted on the PK Analysis Set (PKS). The PKS will consist of all randomized subjects who receive the single dose of trial medication (BI 695501 using autoinjector or BI 695501 using prefilled syringe), and have at least one evaluable primary PK parameter, and are without important protocol deviations or violations thought to significantly affect the PK of BI 695501.

Pharmacokinetic parameters of a subject will be included in the analysis unless the subject has an important protocol violation relevant for the evaluation. Whether a protocol violation is important will be decided no later than in the Report Planning Meeting.

Reasons for exclusion of single pharmacokinetic parameters can for example be:

- Time deviations
- Use of restricted medications
- Dosing errors

It will also be decided in the Report Planning Meeting which subjects are to be included in the PKS.

Details of the presentation and analysis of PK data will be provided in the Trial Statistical Analysis Plan (TSAP).

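### Table 7.7: 2 gives 55% power at gCV 45% and ratio 112%, but the stated design gives about 49%; the other 13 filled cells reproduce

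*Protocol*

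**What the plan says.** Protocol Section 7.7 uses Table 7.7: 2 as its overview of the chance of success under assumed ratios and variabilities. Success means having the "90% confidence interval of the ratio of the gMeans lying within the range of 80-125"%. The caption, "Power (%) for concluding bioequivalence (acceptance range 80-125%) based on a geometric coefficient of variation around 50"%, places the calculation "in a parallel trial (N=160"), and the footnote adds: "The calculations were performed using nQuery Version 2.0.1.0".

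Fourteen cells are filled. The gCV 45% row reads 89%, 83%, 68% and 55% for ratios of 100%, 104%, 108% and 112%. In the 112% column only the gCV 32% cell (71%) and the gCV 45% cell (55%) have values; the gCV 50% and 54% cells are dashes.

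The other inputs are also stated. Section 7.6: "Subjects will be randomized to one of the two treatments in a 1:1 ratio". Section 7.3.1: "The PK endpoints will be log-transformed (natural logarithm) prior to fitting the ANOVA model", with point estimates "and their two-sided 90% CIs will be provided for the overall comparison A versus B". Section 7.7 sets the total "with no planned adjustment for drop-outs".

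**The concern.** The 55% entry breaks the pattern of its own row and column. Between ratios of 104% and 108% the gCV 45% row falls by 15 points. The next step of the same size, towards the upper limit of 125%, would be expected to cost more, but the table shows only 13. The same figure, 55%, also stands in the gCV 54% / ratio 108% cell.

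The table is where a reader looks to see how quickly the chance of success falls if the devices differ or variability is high. The ratio of 112% has a basis in the protocol: Section 7.7 reports it for Cmax in trial 1297.6, the earlier autoinjector-versus-syringe study. If the cell is wrong, the loss of power from gCV 32% to gCV 45% at that ratio is understated, and a scenario that would miss the criterion slightly more often than not is shown as one that would usually meet it.

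**Working it through.** **Inputs**

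- Acceptance limits: ln 0.80 = −0.2231 and ln 1.25 = 0.2231 (Section 7.7).
- Two-sided 90% CI based on the t-distribution, equivalent to two one-sided tests at 5% each (Section 7.3.1).
- N = 160 allocated 1:1, so n = 80 per arm (Sections 7.6 and 7.7); no drop-out allowance. Degrees of freedom 158; t(0.95; 158) = 1.655.
- Log-scale SD: σ = √ln(1 + gCV²). The protocol does not state this conversion; the reproduced cells below support it.

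**Formula**

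Let D be the estimated log ratio, normal with mean ln(ratio) and standard error σ√(2/n), and let S be the sample SD, with 158·S²/σ² following a chi-square distribution on 158 degrees of freedom. Power is the probability that D + t·S√(2/n) < ln 1.25 and D − t·S√(2/n) > ln 0.80, obtained by integrating over the distribution of S.

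**Reproducing the table** (stated value, then exact power in %)

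| gCV | Ratio 100% | 104% | 108% | 112% |
|---|---|---|---|---|
| 32% | >99 / 99.57 | 98 / 98.04 | 90 / 90.38 | 71 / 71.57 |
| 45% | 89 / 89.64 | 83 / 83.99 | 68 / 68.82 | **55 / 48.58** |
| 50% | 81 / 81.65 | 75 / 75.82 | 61 / 61.02 | – / 42.6 |
| 54% | 74 / 74.28 | 68 / 68.80 | 55 / 55.12 | – / 38.5 |

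Thirteen of the 14 filled cells agree within 1 point, and all 13 match when the exact value is truncated to a whole percent. Only gCV 45% / ratio 112% fails: 55 − 48.6 = 6.4 points.

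**The disputed cell by hand**

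- σ = √ln(1 + 0.45²) = √ln 1.2025 = 0.4294.
- Standard error = 0.4294 × √(2/80) = 0.0679.
- CI half-width at that SD = 1.655 × 0.0679 = 0.1124.
- Distance from the true ratio to the upper limit = ln 1.25 − ln 1.12 = 0.2231 − 0.1133 = 0.1098.

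The half-width exceeds the distance. A trial that estimated exactly 112% at this SD would have an upper confidence limit of 1.12 × 1.1189 = 1.253, just outside 125%. About half of all estimates fall above the true ratio, so power has to lie close to, and slightly below, 50%. The lower limit hardly matters at this ratio.

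**Cross-checks on this cell**

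- Noncentral-t calculation: 48.58%.
- Normal approximation: 48.86%.
- 157 degrees of freedom, to allow for the weight covariate: 48.58%.
- Simulation of 1,000,000 trials: 48.5%.

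**Other conventions tried on this cell**

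- SD taken as gCV: 45.6%.
- SD taken as ln(1 + gCV): 58.6%.
- Upper one-sided test only: 48.9%.
- 2.5% per side: 36.1%; 10% per side: 63.0%.
- Ratio 0.88: 40.2%; ratio 1/1.12: 48.6%.

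None gives 55%. Both alternative SD conversions also spoil the other three cells of the row, which match the standard calculation. Reaching 55% at ratio 112% would need a gCV of about 40.5%, or about 97 subjects per arm (194 in total) at gCV 45%.

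**The case against.** The strongest reply concerns importance, not arithmetic. Section 7.7 reports the 112% ratio together with a gCV of 32% (Cmax, 1297.6), and the 45% gCV together with a ratio of 108% (AUC0-∞, 1297.8). The cells for those observed pairs, and for 104% with gCV 54%, all reproduce. The disputed cell combines one endpoint's ratio with another endpoint's variability from another trial, so it is a sensitivity scenario. Relative bioavailability is estimated in an exploratory way, precision is presented first in Table 7.7: 1, and N = 160 is not derived from this cell. The statement that power should exceed 70% rests on an expectation of lower variability; both 55% and 48.6% are below 70%. Nor does the plan attach any decision to the 50% mark.

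All of this stands, and it limits the weight of the point. It does not make the entry correct. The suggestion that 55% was copied from the gCV 54% / ratio 108% cell is conjecture, because the nQuery output is not in the documents. The dashed cells are not errors.

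**Conclusion.** The point holds. Under the stated design, power at gCV 45% and ratio 112% is 48.6%, not 55%: an overstatement of 6.4 points in one of the 14 filled cells. At a ratio of 112%, moving from gCV 32% to gCV 45% takes power from 71% to 48% on the table's truncated scale, where the table shows 71% to 55%.

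The result assumes 80 evaluable subjects per arm, a common log-scale SD of √ln(1 + gCV²), and the 90% CI criterion with limits of 80% and 125%. The agreement of the other 13 cells supports those assumptions. This is a correctable table error with no effect on the sample size, model, limits or planned analyses.

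**What to change.** In Table 7.7: 2, replace 55% with 48% in the gCV 45% / ratio 112% cell; truncation to a whole percent matches the rest of the table. If the sponsor prefers rounding, the entry is 49%, and the other cells should then be rounded too (for example, 83.99% would appear as 84%). The sponsor should confirm the value against the retained nQuery output.

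Filling the two dashed cells is optional. If done, one rule should be used: 42% and 38% truncated, or 43% and 39% rounded, for gCV 50% and 54%.

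The cost is one table entry, with no change to the design, the sample size or the analysis.

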8. INFORMED CONSENT, TRIAL RECORDS, DATA PROTECTION, PUBLICATION POLICY

The trial will be carried out in accordance with the Medical Devices Directive (93/42/EEC) and the harmonised standards for Medical Devices (ISO 14155, current version).

The trial will be carried out in compliance with the protocol, the ethical principles laid down in the Declaration of Helsinki, in accordance with the ICH Harmonized Tripartite Guideline for Good Clinical Practice (GCP), relevant BI Standard Operating Procedures (SOPs), the EU regulation 536/2014 and other relevant regulations.

Standard medical care (prophylactic, diagnostic and therapeutic procedures) remains in the responsibility of the treating physician of the subject.

The Investigator will inform the sponsor immediately of any urgent safety measures taken to protect the trial subjects against any immediate hazard, and also of any serious breaches of the protocol or of ICH GCP*.

The Boehringer Ingelheim transparency and publication policy can be found on the following web page: trials.boehringer-ingelheim.com. The rights of the Investigator and of the sponsor with regard to publication of the results of this trial are described in the Investigator contract. The certificate of insurance cover is made available to the Investigator and the subjects, and is stored in the ISF (Investigator Site File).

8.1 TRIAL APPROVAL, SUBJECT INFORMATION, INFORMED CONSENT

This trial will be initiated only after all required legal documentation has been reviewed and approved by the respective Institutional Review Board (IRB) / Independent Ethics Committee (IEC) and competent authority (CA) according to national and international regulations. The same applies for the implementation of changes introduced by amendments.

Prior to subject participation in the trial, written informed consent must be obtained from each subject according to ICH / GCP and to the regulatory and legal requirements of the participating country. Each signature must be personally dated by each signatory and the informed consent and any additional subject -information form retained by the Investigator as part of the trial records. A signed copy of the informed consent and any additional subject information must be given to each subject.

The Investigator must give a full explanation to trial subjects based on the subjects information form. A language understandable to the subjects should be chosen, technical terms and expressions avoided, if possible. The subjects must be given sufficient time to consider participation in the trial. The Investigator obtains written consent of the subject's own free will with the informed consent form after confirming that the subject understands the contents. The Investigator must sign (or place a seal on) and date the informed consent form.

Boehringer Ingelheim
BI Trial No.: 1297.13
c11534380-01

23 Aug 2016

Trial Protocol

Page 52 of 58

Proprietary confidential information © 2016 Boehringer Ingelheim International GmbH or one or more of its affiliated companies

Re-consenting may become necessary when new relevant information becomes available and should be conducted according to the sponsor's instructions.

The consent and re-consenting process should be properly documented in the source documentation.

8.2 DATA QUALITY ASSURANCE

A quality assurance audit/inspection of this trial may be conducted by the sponsor, sponsor's designees, or by IRB / IEC or by regulatory authorities. The quality assurance auditor will have access to all medical records, the Investigator's trial-related files and correspondence, and the informed consent documentation of this clinical trial.

8.3 RECORDS

Case Report Forms (CRF) for individual subjects will be provided by the sponsor. For drug accountability, refer to [Section 4.1.8](#).

8.3.1 Source documents

In accordance with regulatory requirements the Investigator should prepare and maintain adequate and accurate source documents and trial records that include all observations and other data pertinent to the investigation on each trial subject. Source data as well as reported data should follow good documentation practices and be attributable, legible, contemporaneous, original and accurate. Changes to the data should be traceable (audit trail). Data reported on the CRF must be consistent with the source data or the discrepancies must be explained.

For the CRF, all data must be derived from source documents.

The LabPas and Oracle Clinical (TD Synergy) systems is an electronic data capturing and information management system that will also serve as an e-source system for this trial. The system combines all aspects of source data capturing with process control and clinical trial management. Clinical and laboratory data, except those which are paper based, will be collected in there.

8.3.2 Direct access to source data and documents

The sponsor will monitor the conduct of the trial by regular on-site monitoring visits and in-house data quality review. The frequency of on-site monitoring will be determined by assessing all characteristics of the trial, including its nature, objective, methodology and the degree of any deviations of the intervention from normal clinical practice.

The Investigator /institution will allow on-site trial-related monitoring, audits, IRB / IEC review and regulatory inspections. Direct access must be provided to the CRF and all source documents/data, including progress notes, copies of laboratory and medical test results, which

Boehringer Ingelheim
BI Trial No.: 1297.13
c11534380-01

Trial Protocol

23 Aug 2016

Page 53 of 58

Proprietary confidential information © 2016 Boehringer Ingelheim International GmbH or one or more of its affiliated companies

must be available at all times for review by the CRA, auditor and regulatory inspector (e.g. FDA). The CRA and auditor may review all CRFs and informed consents. The accuracy of the data will be verified by direct comparison with the source documents described in [section 8.3.1](#). The sponsor will also monitor compliance with the protocol and ICH GCP.

8.3.3 Storage period of records

Trial site(s):

The trial site(s) must retain the source and essential documents (including ISF) according to the national or local requirements (whatever is longer) valid at the time of the end of the trial.

Sponsor:

The sponsor must retain the essential documents according to the sponsor's SOPs.

8.4 EXPEDITED REPORTING OF ADVERSE EVENTS

BI is responsible to fulfil their legal regulatory reporting obligation and in accordance to the requirements defined in this CTP.

8.5 STATEMENT OF CONFIDENTIALITY

Individual subject data obtained as a result of this trial is considered confidential and disclosure to third parties is prohibited with the exceptions noted below. Subject privacy will be ensured by using subject identification code numbers.

Data protection and data security measures are implemented for the collection, storage and processing of subject data in accordance with the principles 6 and 12 of the WHO GCP handbook.

Treatment data may be given to the subject's personal physician or to other appropriate medical personnel responsible for the subject's welfare. Data generated as a result of the trial need to be available for inspection on request by the participating physicians, the sponsor's representatives, by the IRB / IEC and the regulatory authorities.

8.5.1 Collection, storage and future use of biological samples and corresponding data

Measures are in place to comply with the applicable rules for the collection, storage and future use of biological samples from clinical trial participants and the corresponding data, in particular

- A Quality Management System has been implemented to ensure the adherence with the Principles of Good Clinical Practice as outlined in 'Note For Guidance On Good Clinical Practice' (CPMP/ICH/13 5/95)
- The facilities storing and analysing biological samples and data from clinical trial participants as well as the laboratories' activities for clinical trials sponsored by Boehringer Ingelheim are regularly audited. The analytical groups and the banking

Boehringer Ingelheim
BI Trial No.: 1297.13
c11534380-01

23 Aug 2016

Trial Protocol

Page 54 of 58

Proprietary confidential information © 2016 Boehringer Ingelheim International GmbH or one or more of its affiliated companies

facility are therefore assessed to be qualified for the storage and use of biological samples and data collected in clinical trials.

- Samples and data are used only if an appropriate informed consent is available.

8.6 TRIAL MILESTONES

The **start of the trial** is defined as the date of the enrolment of the first subject in the whole trial.

The end of the trial is defined as the date of the last visit of the last subject in the whole trial (“Last Patient Out”). **Early termination of the trial** is defined as the premature termination of the trial due to any reason before the end of the trial as specified in this protocol.

Temporary halt of the trial is defined as any unplanned interruption of the trial by the sponsor with the intention to resume it.

Suspension of the trial is defined as an interruption of the trial based on a Health Authority request.

The IEC / competent authority in each participating EU member state will be notified about the trial milestones according to the respective laws.

A final report of the clinical trial data will be written only after all subjects have completed the trial in all countries (EU or non-EU) to incorporate and consider all data in the report.

The sponsor will submit to the EU database a summary of the final trial results within one year from the end of a clinical trial as a whole, regardless of the country of the last subject (EU or non-EU).

Boehringer Ingelheim
BI Trial No.: 1297.13
c11534380-01

23 Aug 2016

Trial Protocol

Page 55 of 58

Proprietary confidential information © 2016 Boehringer Ingelheim International GmbH or one or more of its affiliated companies

